For application of re-examination

TORISEL 25 mg Injection

Special Investigation

— All patient surveillance —

Protocol

Pfizer Japan Inc.

Date of preparation: August 24, 2010, Version 1
Date of revision: February 2, 2011, Versions 2
Protocol ID: B1771015

INTRODUCTION

TORISEL 25 mg Injection (hereinafter called this drug) is a m-TOR inhibitor. This drug acts by inhibiting mTOR (mammalian target of rapamycin), which is a kinase regulating the growth and proliferation of cancer cells. It was granted the marketing authorization in Japan on July 23, 2010 with an indication of metastatic and/or unresectable renal cell carcinoma.

Special Investigation of TORISEL 25 mg Injection - All patient surveillance - (hereinafter called this study) is intended to confirm the effectiveness and safety of this drug in daily clinical settings, examine the onset state of adverse events and potentially influencing factors (particularly, those designated as major investigation items), and examine the onset state and potential onset risk factors of interstitial lung disease. The information obtained in this study shall be used to provide proper-use information, and to prepare documents for the re-examination application. This study, therefore, shall be conducted in strict compliance with the "MHLW Ordinance on the Standard for Post-Marketing Studies and Clinical Trials of Medical Products" (MHLW Ordinance No. 171, dated December 20, 2004). Data obtained from the patients registered in this study will be reported to the MHLW pursuant to the Pharmaceutical Affairs Law, pertinent to which may be publicly posted in MHLW's "Pharmaceutical and Medical Device Safety Information" and "Pharmaceuticals and Medical Devices Information Website (<http://www.info.pmda.go.jp>)" as a listing of patients, which will present the names of drugs, adverse reactions, gender, age (increment of 10 years), and other relevant information. Furthermore, data collected may also be disclosed if the MHLW is required to disclose such information in accordance with the "Act on Access to Information Held by Administrative Organs" (Law No. 42 dated May 14, 1999); provided that in no event will the names of investigators, sites, and other personal information be subject to such disclosure, nor will it be posted or disclosed in any form or shape.

1 OBJECTIVES

The objective of this study is to assess the following subject matters in patients treated with TORISEL 25 mg Injection (hereinafter called this drug) in post-marketing actual use conditions, thereby providing proper-use information.

- (1) To confirm the effectiveness and safety of this drug under actual use conditions
- (2) To examine the onset state of adverse events and potentially influencing factors (particularly, major investigation items)
- (3) To examine the onset state and potential onset risk factors of interstitial lung disease

[Conditions for approval]

A drug use investigation must be conducted with all the patients treated with this drug until the data from a specified number of cases are accumulated after the marketing of this drug in order to understand the background information on patients treated with this drug, collect the data on the safety and effectiveness of this drug as early as possible, and take necessary measures to ensure the proper-use of this drug.

2 PATIENTS

This study will be conducted with all patients treated with this drug in a specific period of time. The indications and dosage and administration of this drug are described below.

[Indications]

Metastatic and/or unresectable renal cell carcinoma

[Precautions Regarding Indications]

1. The efficacy and safety of TORISEL as postoperative adjuvant chemotherapy has not been established.
2. The selection of patients in whom to administer TORISEL must be performed after thorough consideration of the efficacy and safety data based on understanding of information detailed in "Clinical Studies*".

* Refer to the [Clinical Studies] section in the package insert.

[Dosage and Administration]

The usual adult dosage is temsirolimus 25 mg once weekly, to be administered via intravenous infusion over 30 - 60 minutes. The dosage is to be appropriately reduced according to patient's condition.

[Precautions regarding dosage and administration]

1. The efficacy and safety of TORISEL in combination use with other anti-malignant tumor agents including cytokine preparations have not been established.
2. When interstitial lung disease occurs, interrupt/discontinue administration depending on the symptoms and severity with consideration of the following criteria:

Criteria for interruption or discontinuation in case of interstitial lung disease

| Symptom | Intervention |
|---|--|
| Asymptomatic. Only abnormal imaging findings are observed. | Continue to administer. |
| Mild clinical symptoms ^{Note)} (not interfering activity of daily living) | Interrupt administration until the symptoms recovered. |
| Severe clinical symptoms ^{Note)} (interfering with activity of daily living and need oxygen therapy) | Discontinue |
| Aggravation of clinical symptoms and pulmonary diffusing capacity decreased | |
| Underlying pulmonary disease, with changes in clinical or image findings are observed | |

Note: Dyspnea, cough, etc.

3. If severe adverse reactions (Grade 3 or severer) occur other than interstitial lung disease, interrupt administration of TORISEL until resolution of the adverse reaction. If the adverse reaction is resolved within 3 weeks, administration can be resumed at a reduced dose by one level (reduction levels should proceed as follows: initial dose 25 mg -> 20 mg-> 15 mg -> 10 mg).
4. To avoid infusion reactions, an antihistamine (e.g., d-chlorpheniramine maleate, diphenhydramine hydrochloride, etc.) should be administered prior to the administration of TORISEL. If infusion reactions occur, stop administration immediately.
5. When administering TORISEL, do not use infusion kits containing DEHP [di-(2-ethylhexyl) phthalate] as a plasticizer.
6. An in-line filter with a pore size of not greater than 5 μm should be used for TORISEL infusion.
7. Dose reduction should be considered for patients with severe hepatic function disorder.

3 STUDY SIZE

All the patients treated with this drug will be included in the all patient surveillance to be conducted for a specific period of time.

- Target number of cases: 600 cases
- Target number of cases observed: 300 cases treated for 12 weeks or longer (300 cases with Booklet 03 case report form)
(Cases who discontinued the drug before 12 weeks will also be included.)

[Rationale]

The incidence of all the adverse events included in the major investigation items of this study was 1.0% or higher in the drug group of the foreign phase 3 clinical study (304-WW Study). Assuming that the true incidence of an adverse event (particularly an adverse event included in the major investigation items) is 1.0%, 300 cases are required to observe at least 1 case with the event at a probability of at least 95%. The incidence of interstitial lung disease was 17.1% (14/82) in the multinational (Asian) phase 2 clinical study (2217-AP Study).

Assuming that the true incidence of interstitial lung disease is 17.1%, at least 40 cases with the disease can be observed at a probability of at least 95%.

Further, clinical study results showed that interstitial lung disease occurred on Week 4 after the start of the drug or later, and that, in rare cases, some adverse events had an increased incidence or delayed onset as the administration period was prolonged. Considering these results, it was decided to set a target that this study would include 300 cases treated with this drug for 12 weeks or longer.

Clinical study results showed that this drug could be continued for 12 weeks or longer in about 60% of the whole treated cases, with a discontinuance/drop-out rate at 12 weeks of about 40%. Considering that this study will be conducted under actual use condition, it is assumed that the discontinuance/drop-out rate at 12 weeks in this study will be increased by 10% to 50%. That is, it is assumed that this drug will be continued for 12 weeks or longer (the Booklet 03 case report form will be collected) in 50% of the cases included in this study.

Therefore, this surveillance was planned to register 600 cases to collect 300 cases treated with this drug for 12 weeks or longer. In addition, because cases which discontinue the drug before 12 weeks will be included in the study, the case report form will be collected from them to evaluate safety and effectiveness.

4 PLANNED INVESTIGATION PERIOD

Study period*: September 2010 (launch of this drug) to August 2012 (2 years)

Registration period: September 2010 (launch of this drug) to

The cases treated with this drug after the initial 600 cases will be registered, but not studied.

* However, this study will be conducted until March 2014 when the separate Special Investigation on long-term use is included (cumulative study period: 3 years and 6 months).

5 STUDY PROCEDURES

5.1 Study method

This study will be conducted with all the patients treated with this drug until the data from a specified number of cases are accumulated after the marketing of this drug in order to understand the background information on patients treated with this drug, collect data on the safety and effectiveness of this drug as early as possible, and take necessary measures to ensure the proper-use of this drug. This study will be conducted as all patient surveillance system at sites with investigators who have sufficient knowledge and experience about drug therapy for renal cancer.

(1) Conduct of prior explanation

Medical representatives (MRs) will explain the safety and effectiveness of this drug to investigators and pharmacists expected to use the drug using the materials for providing safety information.

[Materials for providing safety information]

- Package insert
- Explanation to "Precautions for Use" of new drugs
- Interview Form
- Proper-use guide
- Summary of general product information

(2) Study contract

After the prior explanation, a contract will be made with each site on this study. A specific contract form of a site, if any, will be used. This drug will be supplied to each site after the contract with the institution is made.

5.2 Data collection method

In this study, the case report form provided by the sponsor will be used to collect data when the sponsor asks sites to use it. When the sponsor asks sites to use the specific case report form to collect data, the investigator in each site will readily fill in the form and submit it to the sponsor.

5.3 Patient registration

(1) Registration procedure

The investigator will complete the registration form on patients treated with this drug provided by sponsor, and submit the form to Patient Registration Center via FAX at treatment.

[TORISEL Patient Registration Center]

[contact] (available 24 hours)

Business hours: 9:00 to 18:00*

(except for Saturdays, Sundays, National Holidays, and New Year Holidays)

*FAX transmission after 17:30 will be responded by 9:30 on the following business day.

(2) Case registration

After the patient was registered, "the announcement of the patient registration" will be sent to the investigator by FAX. Investigator will save the announcement in the site.

If there is something to be confirmed found in the registration form, confirmation will be requested with the investigator. In the case of confirmation, "request form of confirmation" and "registration form (copy)" will be sent from the Registration Center to the investigator by FAX.

(3) Confirmation of registered case

At the end of the registration period, each investigator will confirm that all his/her cases treated with this drug are listed in the "TORISEL Special Investigation Registration List," and submit it to MR in charge with his/her signature or print of his/her name with his/her seal.

When an investigator finds a case treated with the drug, but not registered in the list, the investigator will readily register the case.

5.4 Observation period

The observation period for this study will be set until Week 24 after the start of administration (cases treated with the drug for more than 25 weeks will be included in the separately planned Special Investigation on long-term use and observed for up to 96 weeks after the start of administration)

[figure not shown]
Clinical evaluation of tumor: Weeks 8, 16, and 24. For discontinued cases, if the clinical evaluation of tumor is not performed within 4 weeks prior to discontinuation, clinical evaluation of tumor will be performed at the time of discontinuation.

Adverse events: Until Week 24 after the start of administration. If the drug is discontinued before Week 24, observe until Day 28 after the discontinuation of administration.

This study will be conducted using a case report form divided into separate booklets. The results during the following observation periods will be recorded in the different booklets of the case report form.

| Booklet | Observation period |
|------------|---|
| Booklet 01 | Start of administration to Week 4 (Day 28) |
| Booklet 02 | Week 5 (Day 29) to Week 12 (Day 84) after start of administration |
| Booklet 03 | Week 13 (Day 85) to Week 24 (Day 168) after start of administration |

(Start of administration)
(Day 1)

Observation period and evaluation time points for each booklet of case report form

5.5 Reminders concerning completing, revising, and reviewing of case report forms

- (1) The investigator shall, upon confirming the study items, complete the case report form based on medical charts and other medical records such as relevant test results, using a pen, ballpoint pen, or other inerasable means.
- (2) When the investigator receives an inquiry from Pfizer Japan Inc. (for data confirmation), he/she will reconfirm the above medical records and, if necessary, correct and re-submit the case report form. When the investigator corrects a part of the case report form, he/she will draw a double line on the part so that the original entry is kept visible and put a correction seal. When the confirmation investigator corrects a part related to evaluation of effectiveness or safety, in principle, he/she will record the reason and date of correction.

6 INVESTIGATION ITEMS AND SCHEDULE

The investigator will conduct the study according to the following schedule of observation. After the conclusion of the study contract, the investigator will register patients who meet the registration conditions, check their data including the background information at the start of administration, and fill in the case report form (at patient registration and at the start of administration). In the observation period, the investigator will check their follow-up data at the end of the observation period of each booklet of the case report form or at discontinuation when the drug is discontinued, record the data to the case report form and submit it to the sponsor.

[Observation schedule]

| | | Observation and evaluation time points | | | |
|--|--|--|--|---|--|
| | | At the start of administration | Starting date of administration to Week 4 (Day 28) | Weeks 5 to 12 after start of administration | Weeks 13 to 24 after start of administration |
| Registration information | ID number, patient initials, gender, date of birth (age), scheduled date to start administration, and availability of pre-treatment chest CT | ● | | | |
| Patient background | | ● | | | |
| Clinical history | | ● | | | |
| Prior treatment history | | ● | | | |
| Record of TORISEL treatment | | | ↔ | ↔ | ↔ |
| Concomitant therapy (drug therapy) | | | ↔ | ↔ | ↔ |
| Concomitant therapy (non-drug therapy) | | | ↔ | ↔ | ↔ |
| Examination (chest CT) | | ● | ● | ● | ● |
| Examination (chest X-rays) | | ● | ● | ● | ● |
| Examination (clinical laboratory testing) | | ● | ● | ● | ● |
| Effectiveness evaluation* | | | | Week 8 | Week 16 Week 24 |
| Pregnancy status | | | ● | ● | ● |
| Patient summary (continuation/discontinuation status) | | | ● | ● | ● |
| Adverse events | | | ↔ | ↔ | ↔ |
| Detailed information on adverse events related to interstitial lung disease (Attachment: detailed case report form) | | | ↔ | ↔ | ↔ |

* For discontinued cases, if the clinical evaluation of tumor is not performed within 4 weeks prior to discontinuation, clinical evaluation of tumor will be performed at the time of discontinuation.

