The progress of the target malignant tumor will not be recorded as an adverse event. However, any malignant tumor that reaches a lethal outcome during the observation period has to be recorded as an adverse event. When a patient starts a new treatment, the reportable period of the event will end when the new treatment is started.

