### **2.1.2. Long-term Use Surveillance**

This study is a non-interventional study in a cohort of patients who were registered in the all patient surveillance and received this drug for unresectable or metastatic renal cell carcinoma for more than 24 weeks.

*Among the patients registered and treated in the all patient surveillance, those to be continuously treated with this drug for more than 24 weeks will be included in this study. That is, the target number of cases to be registered in the all patient surveillance is 600 (rationale stated in the protocol of the all patient surveillance) and those to be continuously treated for more than 24 weeks will be registered again in this study. Therefore, no definite target number of cases is set for this study. However, the expected number of cases to be registered in this study is shown below and considered as the target number of cases to be registered.*

*Expected number of cases: about 120 cases*

*[Rationale]*

*The expected number of cases to be registered in this study is described. In the clinical trials, (304-WW and 2217-AP Studies), about 35% of the subjects could be continuously treated for 24 weeks or longer, with a discontinuance/drop-out rate at 24 weeks being about 65%. Considering that the all patient surveillance will be conducted under actual use condition, and that it is necessary to re-register from all patient surveillance to this study, it is assumed that the discontinuance/drop-out rate at 24 weeks in the all patient surveillance will be further increased by 15% to 80%. That is, it is assumed that 20% of the cases included in the all patient surveillance will be registered in this study after the completion of the all patient surveillance. It is therefore expected that about 120 cases will be registered in this study when 600 cases will be registered in the all patient surveillance. However, the actual number of cases registered may be different from the expected number because it depends on the conditions and results of the all patient surveillance.*

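### Protocol 5.4 observes adverse events to Day 28 after discontinuation, but Section 6 has the case report form submitted at discontinuation, which risks under-capture of post-treatment events

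*Protocol*

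**What the plan says.** **Observation window.** Protocol 5.4, on adverse events: "If the drug is discontinued before Week 24, observe until Day 28 after the discontinuation of administration".

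**Submission.** Protocol 6 has follow-up data checked at the close of each booklet period "or at discontinuation when the drug is discontinued, record the data to the case report form and submit it to the sponsor". The schedule table has no column for the time after discontinuation. Its footnote covers tumour evaluation in discontinued patients but not adverse events.

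**Safety evaluation date.** Protocol 6.8 follows each event, in principle, to each safety evaluation date. Sections 6.3 and 6.6 use that date as the end of recording, and 6.7 uses it to decide whether treatment continues. No section places it relative to discontinuation.

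**Separate reporting.** Section 6.8 also asks for prompt notification of the sponsor, follow-up in principle to resolution, and a telephone call within 24 hours for serious events. Section 6.8.1 adds a detailed form for interstitial lung disease (ILD).

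**Booklets.** In 5.4, Booklet 02 covers "Week 5 (Day 29) to Week 12 (Day 84) after start of administration" and Booklet 03 covers "Week 13 (Day 85) to Week 24 (Day 168) after start of administration". Section 3 sets the target as "300 cases treated for 12 weeks or longer (300 cases with Booklet 03 case report form").

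**Stopping rates.** Protocol 3: "it is assumed that the discontinuance/drop-out rate at 12 weeks in this study will be increased by 10% to 50" percent. SAP 2.1.2, on the clinical trials: "with a discontinuance/drop-out rate at 24 weeks being about 65" percent. For the surveillance, SAP 2.1.2 assumes 80%, which also allows for patients who are not re-registered.

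**The concern.** A site that follows Section 6 to the letter sends in the form on the day the 5.4 window opens. A site that follows 5.4 waits 28 days. Both can claim to be following the protocol, so capture of post-treatment events may differ by site for reasons unrelated to the drug.

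Safety, and ILD in particular, is a stated objective. SAP 8.2.6 tabulates incidence as the number of patients with an event, and SAP 7 has no missing-data handling, so an event that was never entered counts as no event. The affected patients include those who stopped because of an adverse event (a listed reason in Protocol 6.7). The analysis also expects data from this period: the progression-free survival definition in SAP 6.2 includes 28 days after the end of treatment.

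There is a second, smaller problem. Section 3 treats receipt of Booklet 03 as equivalent to at least 12 weeks on drug. If Booklet 03 is also used for post-treatment follow-up of patients who stopped earlier, that equivalence fails.

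**Working it through.** **1. The plan's own figure.** Target of 300 patients treated at least 12 weeks, with 50% stopping before then (Protocol 3): 300 / (1 − 0.50) = 600. Reproduced.

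**2. Patients with a post-treatment window.**
- By Week 12: 600 × 0.50 = 300.
- By Week 24, trial rate: 600 × 0.65 = 390.
- By Week 24, surveillance assumption: 600 × 0.80 = 480. This is an upper figure, because it includes failure to re-register.

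**3. The two rules side by side.** For a patient who stops on Day T, 5.4 observes to Day T + 28, while Section 6 records and submits at Day T. The difference is the whole 28 days.

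**4. Where the window falls.** The booklets count days since the start of administration, not days on drug.
- T = 1–28: the window ends on Days 29–56, in Booklet 02.
- T = 29–56: it ends by Day 84, inside Booklet 02.
- T = 57–84: it ends on Days 85–112, in Booklet 03, although the patient was treated for no more than 12 weeks. Example: 70 + 28 = Day 98, past Day 84.
- T = 85–140: it ends by Day 168, inside Booklet 03.
- T = 141 up to Week 24: it ends after Day 168, where this study has no booklet.

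**5. Rough size of each group.** Assumption: a constant stopping hazard within Weeks 1–12 and within Weeks 13–24. With s12 and s24 the proportions still on drug, S(d) = s12^(d/84) up to Day 84, then s12 × (s24/s12)^((d−84)/84).

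For 50% stopping by Week 12 and 65% by Week 24:
- S(28) = 0.7937, so 600 × 0.2063 = 124 stop in Weeks 1–4.
- S(56) = 0.6300, so 600 × (0.6300 − 0.5000) = 78 stop in Weeks 9–12.
- S(140) = 0.3942, so 600 × (0.3942 − 0.3500) = 27 stop after Day 140.

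| Stopped by Week 12 / 24 | Stoppers | Weeks 1–4, crosses into Booklet 02 | Weeks 9–12, crosses into Booklet 03 | After Day 140, passes Day 168 | Window inside own booklet | Window ends by Day 168 |
|---|---|---|---|---|---|---|
| 40% / 65% | 390 | 94 | 67 | 41 | 188 (48%) | 89% |
| 50% / 65% | 390 | 124 | 78 | 27 | 162 (42%) | 93% |
| 50% / 80% | 480 | 124 | 78 | 43 | 235 (49%) | 91% |

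Rows may differ by one through rounding.

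**6. Share of time.** Complete windows add at most 390 × 28 / 365.25 = 29.9 patient-years, or 480 × 28 / 365.25 = 36.8. On-treatment time to Week 24 in the three scenarios is 172.6, 158.1 and 145.4 patient-years. The window is therefore 29.9/202.5 = 14.8%, 29.9/188.0 = 15.9% and 36.8/182.2 = 20.2% of the combined time. Death or a new treatment would shorten it. These are shares of time, not of events.

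**The case against.** The best reply is that 5.4 is the specific rule and Section 6 is a general sentence about completing forms within the observation period that 5.4 defines. Nothing prevents the safety evaluation date from being Day 28 after discontinuation, and 6.7 can be read as recording treatment status as of that date. Death, and ILD or infection that needs hospital admission, are serious by the definition in 6.8 and go by telephone whatever the state of the booklet. The observation-period figure in 5.4 and the text of the Adverse Event Reporting attachment were not available for this review, and either may state how late events are entered.

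Most of this stands as a limit on size. It does not remove the conflict. Whatever the figure or attachment says, the Section 6 wording still places submission at discontinuation. The resubmission route in 5.5 depends on a sponsor inquiry, so it is not a planned second collection. The documents do not say how separately notified events reach the case report form tabulations.

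The objection that the booklet count is only operational also has force, since dosing dates are recorded (6.2) and 12-week exposure can be derived from them. That is why changing the definition of the target is cheap.

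A reader might also infer a further cut-off from the sentence in 6.8 "When a patient starts a new treatment, the reportable period of the event will end when the new treatment is started". It follows text on fatal tumour progression, and its reach is unclear. Ending reporting at a new treatment is an ordinary attribution choice, so no change is asked for here.

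**Conclusion.** The protocol contradicts itself on when adverse event recording ends for discontinued patients, and this should be corrected. Followed literally, Section 6 risks under-capture, differing by site, of events that start in the 28 days after stopping, mainly non-serious ones. On the documents' rates, about 50% of patients have such a window by Week 12 and at least about 65% by Week 24. The form gaps are narrower: windows that cross into a later booklet, and stops after Day 140. Their sizes in the table rest on the assumed hazard shape.

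Four stronger readings are not supported:
- *Post-treatment events are lost.* Section 6.8 has its own notification and follow-up route, with a 24-hour call for serious events.
- *The booklets do not cover the window.* It ends by Day 168 for about nine in ten of those who stop.
- *Forty percent of observation is lost.* With stops spread evenly over Days 1–84 (mean about 42), 28 / (42 + 28) = 40%. That applies only to stops before Week 12, with every form closed at discontinuation and no death or new treatment.
- *Incidence is biased downward most where risk is highest.* The documents give no event rates for the window, so neither the size nor the pattern of any bias can be derived.

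**What to change.** - Reconcile Protocol 6 and 6.8 with 5.4. For discontinued patients, have the adverse event section completed and submitted after the 5.4 window closes (Day 28 after discontinuation, or death if earlier).
- State that these entries go in the last open booklet, even if that date passes the booklet's nominal end. This covers both the windows that cross booklets and the stops after Day 140.
- If the change is made by defining the safety evaluation date, check 6.3, 6.6 and 6.7, which use the same date.
- Count the 300-case target from the recorded dosing dates, not from receipt of Booklet 03.

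The cost is wording in the protocol and the form instructions, and forms for discontinued patients arriving up to four weeks later. That works somewhat against the aim of collecting data early (Protocol 1 and 5.1), although serious events would still come in by telephone. The figures of 600 and 300 do not change.
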